8.2 DATA QUALITY ASSURANCE

A quality assurance audit/inspection of this trial may be conducted by the Sponsor, Sponsor's designees, or by IRB / IEC or by regulatory authorities. The quality assurance auditor will have access to all medical records, the Investigator's trial-related files and correspondence, and the informed consent documentation of this clinical trial.

8.3 RECORDS

Case Report Forms (e)CRF for individual patients will be provided by the Sponsor. See [section 4.1.5.2](#) for rules about emergency code breaks. For drug accountability, refer to [section 4.1.8](#).

8.3.1 Source documents

Source documents provide evidence for the existence of the patient and substantiate the integrity of the data collected. Source documents are filed at the investigator's site.

Data entered in the eCRFs that are transcribed from source documents must be consistent with the source documents or the discrepancies must be explained. The investigator may need to request previous medical records or transfer records, depending on the trial; also current medical records must be available.

For eCRFs all data must be derived from source documents.

8.3.2 Direct access to source data and documents

The Investigator / institution will permit trial-related monitoring, audits, IRB / IEC review and regulatory inspection, providing direct access to all related source data / documents. CRF/eCRF and all source documents, including progress notes and copies of laboratory and medical test results must be available at all times for review by the Sponsor's clinical trial monitor, auditor and inspection by health authorities (e.g. Food and Drug Administration (FDA)). The Clinical Research Associate (CRA) / on site monitor and auditor may review all CRF / eCRF, and written informed consents. The accuracy of the data will be verified by reviewing the documents described in [section 8.3.1](#).

8.4 LISTEDNESS AND EXPEDITED REPORTING OF ADVERSE EVENTS

8.4.1 Listedness

To fulfil the regulatory requirements for expedited safety reporting, the sponsor evaluates whether a particular adverse event is "listed", i.e. is a known side effect of the drug or not. Therefore a unique reference document for the evaluation of listedness needs to be provided. For the BI 836880 this is the current version of the Investigator's Brochure ([c02353882-01](#)). The current version of this reference document is to be provided in the ISF. No AEs are classified as listed for study design, or invasive procedures.

8.4.2 Expedited reporting to health authorities and IEC / IRB

Expedited safety reporting (7/15 days reports) at a site will end 30 days after the trial drug was permanently discontinued for the last patient at that site.

8.6 END OF TRIAL

The trial will end when the last patient has completed the EoR visit as specified in [Section 6.2.3.4](#) and [6.2.3.5](#). The IEC / competent authority in each participating EU member state needs to be notified about the end of the trial or early termination of the trial.

10. APPENDICES

10.1 INSTRUCTIONS FOR USE

10.1.1 Instructions for Pharmacists

Available in ISF.

10.2 BLOOD PRESSURE MEASUREMENT PROCEDURE

[figure not shown]
The preferred method of blood pressure measurement is by a standard mercury sphygmomanometer. If a standard mercury sphygmomanometer is not available, alternative devices according to website dableducational.org may be used. At screening, blood pressure should be taken in both arms. If the pressures differ by more than 10 mmHg (as in the presence of a subclavian steal syndrome), the arm with the higher pressure (either systolic or - if needed to decide - diastolic) should be used for subsequent measurements. Blood pressure measurements should be performed on the same arm and, if possible, by the same person. The same method and device must be used throughout the trial for a patient i.e. if a patient receives the first blood pressure measurement for example with an electronic device, the same method and device should be used throughout the study for this patient (without switching to manual blood pressure measurement). On the other hand, inter-patient variability is acceptable, i.e. a study site is allowed to consistently use an electronic device to measure the blood pressure in a given patient throughout the study and a manual technique in another patient. After patients have rested quietly, in the seated position for five minutes, three blood pressure measurements will be taken two minutes apart and all three results have to be entered in the eCRF. The seated pulse rate will be taken during the two-minute interval between the second and third blood pressure reading. Blood pressure measurements should be recorded to the nearest 2 mmHg only when measured with a manual sphygmomanometer; when digital devices are used the value from the device should be rounded to the nearest 1 mmHg. For calculation of mean values, decimal places should be rounded to integers (e.g. a DBP of 94.5 would be rounded to 95 mmHg and a DBP of 109.4 would be rounded to 109 mmHg). The above mentioned procedure is considered as standardised conventional blood pressure measurement (CBPM).

In case of a suspected “white coat effect” it is recommended to repeat the measurement in an pleasant condition after sufficient rest. Ambulatory blood pressure measurement (ABPM) can be an option in specific cases to observe BP profiles over a longer period (e.g. during infusion and thereafter) and even outside the hospital in private surrounding. However treatment decisions should be based whenever possible on CBPM as described above and ABPM should be used for observation only. In case BP values from ABPM should be used for treatment related decisions, this has to be taken from appropriate timepoints and validated ABPM devices according to website dableducational.org should be used. Values from self blood pressure measurement (SBPM) communicated from patient to investigator is not considered valuable for study related decisions.

[figure not shown]
10.3 PHARMACOKINETIC ANALYSES

If data allow, the following pharmacokinetic parameters of BI 836880 will be evaluated using noncompartmental analysis methods according to the internal BI [REDACTED]

[figure not shown]
After the first dose:

- AUC_{0-168} (area under the plasma concentration-time curve over the time interval from 0 to 168h).

- $t_{1/2}$ (terminal half-life).

Pharmacokinetic parameters will be calculated using noncompartmental analysis (NCA). The derivation of pharmacokinetic parameters is described in detail in [REDACTED]

Proprietary confidential information © 2019 Boehringer Ingelheim International GmbH or one or more of its affiliated companies

**10.4 BLOOD SAMPLING TIME POINTS FOR PK, [REDACTED] AND
 ECG RECORDING IN THE PHASE I PART OF THE STUDY
 (DOSE ESCALATION PHASE)**

Table 10.4: 1 Blood sampling scheme for PK, [REDACTED] in courses 1, 2, 3 and from course 4 onwards

Course	Visit	Day	Time Point (hh:min)	CRF Time / planned time	PK: BI 836880	[REDACTED]	ECG	BP
1***	V1	1	Before start of BI 836880 infusion	-0:05	x	[REDACTED]	X (3x)	X (3x)
			Start of BI 836880 infusion	0:00		[REDACTED]		
			Before end of infusion	1:30**		[REDACTED]	X (3x)	X (3x)
			Immediately after end of infusion*	1:30**	x	[REDACTED]		
			0.5h after the end of infusion	2:00	x	[REDACTED]		
			1.5h after the end of infusion	3:00	x	[REDACTED]		
			3.5h after the end of infusion	5:00	x	[REDACTED]		
			6.5h after the end of infusion	8:00	x	[REDACTED]		
		2		24:00	x	[REDACTED]	X (3x)	X (3x)
		3	48h after the end of infusion	48:00	x	[REDACTED]		X (3x)
	V2	8		168:00	x	[REDACTED]		X (3x)
V3	15			336:00	x	[REDACTED]		X (3x)

Proprietary confidential information © 2019 Boehringer Ingelheim International GmbH or one or more of its affiliated companies

Table 10.4: 1(cont'd) Blood sampling scheme for PK, [REDACTED] in courses 1, 2, 3 and from course 4 onwards (cont.)

Course	Visit	Day	Time Point (hh:min)	CRF Time / planned time	PK: BI 836880		ECG	BP
2	V1	1	Before start of BI 836880 infusion	-0:05	x		X (3x)	X (3x)
			Start of BI 836880 infusion	0:00				
			Before end of infusion	1:30**			X (3x)	X (3x)
			Immediately after end of infusion*	1:30**	x			
			0.5h after the end of infusion	2:00	x			
			1.5h after the end of infusion	3:00	x			
			3.5h after the end of infusion	5:00	x			
			6.5h after the end of infusion	8:00	x			
		2		24:00	x		X (3x)	X (3x)
		3	48h after the end of infusion	48:00	x			X (3x)
	V2	8		168:00	x			X (3x)
	V3	15		336:00	x			X (3x)
3	V1	1	Before start of BI 836880 infusion	-0:05	x		X (3x)	X (3x)
			Start of BI 836880 infusion	0:00				
			Before end of infusion	1:30**			X (3x)	X (3x)
			Immediately after end of infusion*	1:30**	x			
		2		24:00	x			X (3x)

Proprietary confidential information © 2019 Boehringer Ingelheim International GmbH or one or more of its affiliated companies

Table 10.4: 1(cont'd) Blood sampling scheme for PK, [REDACTED] in courses 1, 2, 3 and from course 4 onwards (cont.)

Course	Visit	Day	Time Point (hh:min)	CRF Time / planned time	PK: BI 836880	[REDACTED]	ECG	BP
4	V1	1	Before start of BI 836880 infusion	-0:05	x	[REDACTED]	X (3x)	X (3x)
			Start of BI 836880 infusion	0:00		[REDACTED]		
			Before end of infusion	1:30**		[REDACTED]	X (3x)	X (3x)
			Immediately after end of infusion*	1:30**	x	[REDACTED]		
			0.5h after the end of infusion	2:00	x	[REDACTED]		
			1.5h after the end of infusion	3:00	x	[REDACTED]		
			3.5h after the end of infusion	5:00	x	[REDACTED]		
			6.5h after the end of infusion	8:00	x	[REDACTED]		
		2		24:00	x	[REDACTED]	X (3x)	
	V2	8		168:00	x	[REDACTED]		X (3x)
	V3	15		336:00	x	[REDACTED]		X (3x)
5-12	V1	1	Before start of BI 836880 infusion	-0:05	x	[REDACTED]	X (3x)	X (3x)
			Start of BI 836880 infusion	0:00		[REDACTED]		
			Before end of infusion	1:30**		[REDACTED]	X (3x)	X (3x)
EOT***					x	[REDACTED]	X (3x)	X (3x)
EoR***					x	[REDACTED]		X (3x)
FU1***					x	[REDACTED]		

* within 5 min after the end of infusion

** PTM of 1:30 according to an infusion duration of 90 min. If the infusion duration should be shorter (or longer), the PK sample has to be taken in any case immediately after the end of the infusion/ the ECG has to be conducted shortly before end of infusion and the actual sampling time needs to be recorded in the eCRF. Subsequent PK samples (in C1, C2 and C4) have to be taken 0.5h, 1.5h, 3.5h and 6.5h after the end of the infusion.

*** in case of an intra-patient dose escalation the 1st cycle with the higher dose will follow cycle one at the start of treatment with BI 836880 with regards to sampling, (PK, [REDACTED])

**** No samples will be collected after data base lock and the trial is completed (see [Section 6.2.3.5](#))

10.6 STATISTICAL APPENDIX INCLUDING MODEL PERFORMANCE AND DATA SCENARIOS

The model was assessed by two different metrics: hypothetical on-study data scenarios and long-run operating characteristics.

Hypothetical data scenarios

Hypothetical data scenarios are shown in [Table 10.6: 1](#). These scenarios reflect potential on-study data constellations and related escalation as allowed by the model and the 200% escalation limit or doses of interest. For each scenario, the probability of overdose for the current dose, as well as the next potential dose and related probabilities of under-dosing, target dose and over-dosing are shown. A new cohort will be open for enrolment after the review on data from the previous cohort is completed by DSB.

For example, scenario 1 represents the case that no DLT is observed in two patients at the starting dose of 40mg. In this case, the next dose permitted by the model and by the 200% escalation rule is 120mg. Scenario 4 represents the case that no DLTs are observed in the first cohort of two patients at 40mg, and 1 DLT is observed in the second cohort of three patients at 120mg. In this case, the model requires to re-enroll at the current dose level of 120mg. Scenario 5 shows the case that 2 DLTs are observed in the second cohort of three patients at 120mg. The model then allows a de-escalation.

Finally, scenario 6 and 7 illustrate the case where no DLTs are seen in the first three cohorts. In scenario 6, no DLT is observed at 720mg, either. However, the model does not allow the escalation to 1250mg for safety concerns despite the fact that no DLTs are observed in the first four cohorts. On the other hand, scenario 7 presents the case that 1 DLT is seen at 720mg. In this case, no escalation to 1250mg is allowed as well. These two cases illustrate the adaptive behaviour of the model even in extreme situations.

Table 10.6: 1 Hypothetical data scenarios.

Scenario	Cohort	Dose (mg)	# DLT	# Pat	Current Dose: P(OD)	Next Dose	Next Dose		
							P(UD)	P(TD)	P(OD)
1	1	40	0	2	0.013	120	0.894	0.062	0.044
2	1	40	1	3	0.278	N/A	N/A	N/A	N/A
3	1	40	0	2					
	2	120	0	2	0.013	360	0.816	0.103	0.081
4	1	40	0	2					
	2	120	1	3	0.194	120	0.497	0.309	0.194
5	1	40	0	2					
	2	120	2	3	0.575	40	0.434	0.330	0.236
6	1	40	0	2					
	2	120	0	2					
	3	360	0	3					
	4	720	0	3	0.025	720	0.878	0.097	0.025
7	1	40	0	2					
	2	120	0	2					
	3	360	0	3					
	4	720	1	3	0.224	720	0.436	0.340	0.224

Operating characteristics

Operating characteristics are a way to assess the long-run behaviour of a model. Under an assumed true dose-toxicity curve, metrics such as the probability of recommending a dose with true DLT rate in the target interval can be approximated via simulation. [Table 10.6: 2](#) describes 5 assumed true dose-toxicity scenarios which were used to assess the operating characteristics of the model. These scenarios reflect a wide range of possible cases as follows:

- Scenario 1: aligned with prior medians
- Scenario 2: high-toxicity scenario
- Scenario 3: low-toxicity scenario
- Scenario 4: low-tox followed by high-tox
- Scenario 5: non-logistic dose-toxicity scenario

Table 10.6: 2

Assumed true dose-toxicity scenarios

Scenario		Dose (mg)				
		40	120	360	720	1250
1 (Prior)	P(DLT)	0.069	0.104	0.176	0.274	0.444
2 (High Tox)		0.100	0.204	0.371	0.500	0.603
3 (Low Tox)		0.001	0.006	0.039	0.180	0.250
4 (Non-Logistic)		0.040	0.180	0.280	0.360	0.380
5 (Low-High)		0.001	0.010	0.180	0.317	0.600

For each of these scenarios, 1000 trials were simulated. It was then assessed how often a dose was declared as MTD with true DLT rate in the under-, targeted or over-dose range. Furthermore, the average, minimum and maximum number of patients per trial and the average number of DLTs per trial are reported. Results are shown in Table 10.6: 3.

Table 10.6: 3

Simulated operating characteristics

Scenario	% of trials declaring an MTD with true DLT rate in				# Patients	# DLT
	underdose	target dose	overdose	STOPPED	Mean (Min-Max)	Mean (Min- Max)
1	22.7	61.6	0.2	15.5	17.05 (3 – 34)	2.896 (1 – 10)
2	9.5	52.0	14.8	23.7	15.38 (3 – 30)	3.642 (1 – 10)
3	26.2	73.8	0	0	19.77 (16 – 36)	2.236 (1 – 6)
4	5.5	79.2	5.7	9.6	17.78 (3 – 35)	3.664 (1 – 10)
5	14.4	85.4	0.2	0	19.60 (15 – 40)	3.303 (1- 8)

In scenario 1, which reflects the case that the true dose-toxicity is aligned with prior medians, 61.6% of the simulated trials declared a dose as MTD with true DLT rate in the targeted dose range. Note that 15.5% of the simulated trials stop because of high toxicity. This is mostly due to the cases that 1 DLT is observed out of 3 patients at the starting dose 40mg. In reality, this situation would rarely happen as the safety profile of starting dose is expected to be good. In addition, dose escalation could still happen after the discussion within DSB.

In scenario 2 (high-toxicity scenario), the starting dose has already >10% probability of observing at least 2 DLTs out of 3 patients or 1 DLT out of 2 patients in the first cohort. This contributes to the high percentage (23.7%) of all simulated trials for which the trial is stopped

since none of the doses is considered tolerable anymore. This is an expected situation for a high-toxicity scenario.

In scenarios 3, 4 and 5, more than 50% of the simulated trials declared a dose as MTD with true DLT rate in the targeted dose range.

The mean patient numbers range from 15.4 patients (high-toxicity scenario) to 19.8 patients (low-toxicity scenario) and the maximum number of patients was 40. Therefore, the patient numbers are as expected and increase when moving away from the high-toxicity scenario. In summary, the considered data scenarios show a reasonable behavior of the model and the operating characteristics demonstrate a good precision of MTD determination.

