A summary of the prior distribution is provided in [Table 7.1:1](#). Additionally, the prior probabilities of DLT at different doses, as well as the corresponding probability of under-, targeted and overdosing, are shown in [Table 7.1:2](#). Graphically, the prior medians with accompanying 95% credible intervals are shown in [Figure 7.1:1](#). As can be seen from both, the Table and the Figure, the prior medians of the DLT probabilities are in-line with the prior medians derived from the weakly informative prior, and the uncertainty around the medians is large, showing the low amount of information this prior provides. This is also supported by the prior sample size, i.e. the information contained in the prior. This is approximately equal to 1.2 patients, i.e. less than or around half of the weight the first cohort in the study will have.

Table 7.1: 1 Summary of prior distribution

Prior Component	Mixture Weight	Mean vector	SD vector	Correlation
1: Weakly inf.	0.900	-0.333 0.647	2.000, 1.000	0.000
2: High Tox	0.050	0.419 -0.274	2.000, 1.000	0.000
3: Low Tox	0.050	-3.316 0.042	5.000, 0.010	0.000

Table 7.1: 2 Prior probabilities of DLT at selected doses

Dose	Probability of true DLT rate in			Mean	SD	Quantiles		
	[0–0.16)	[0.16–0.33)	[0.33–1]			2.5%	50%	97.5%
40	0.877	0.049	0.074	0.069	0.172	<.001	0.001	0.703
120	0.813	0.071	0.116	0.104	0.208	<.001	0.006	0.812
360	0.685	0.110	0.205	0.176	0.258	<.001	0.043	0.899
720	0.515	0.153	0.332	0.274	0.295	<.001	0.148	0.944
1250	0.269	0.164	0.566	0.444	0.318	0.005	0.410	0.975

Doses printed in bold face meet the overdose criterion ($P(\text{overdose}) < 0.25$)

[figure not shown]

Figure 7.1: 1 Prior medians and 95% credible intervals

The MTD may be considered reached if the following criteria is fulfilled

1. At least 1 DLT on the trial and either
2. At least 6 patients haven been treated at the MTD and the posterior probability of the true DLT rate in the target interval (16%-33%) is above 50%, OR
3. At least 18 patients in the trial with 6 patients have been treated at MTD.

Statistical model assessment

The model was assessed using two different metrics:

1. Hypothetical data scenarios: for various potential data constellations as they could occur in the actual trial, the maximal next doses as allowed by the model and by the 100% escalation limit are investigated. Data scenarios thus provide a way to assess the “on-study” behaviour of the model.

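### The operating-characteristics scenario described as the prior medians uses the prior means; two scenario names are swapped in the list, and the model tables were not updated for the 1000 mg level

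*Protocol*

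**What the plan says.** Protocol section 10.6 introduces five assumed dose-toxicity curves. The first is "Scenario 1: aligned with prior medians", and the text below Table 10.6:3 repeats this: "In scenario 1, which reflects the case that the true dose-toxicity is aligned with prior medians, 61.6% of the simulated trials declared a dose" in the target range. It continues: "Note that 15.5% of the simulated trials stop because of high toxicity", with the reason "This is mostly due to the cases that 1 DLT is observed out of 3 patients at the starting dose 40mg".

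Section 7.1 uses the term prior medians for Table 7.1:2 ("Prior probabilities of DLT at selected doses"), stating that "the prior medians of the DLT probabilities are in-line with the prior medians derived from the weakly informative prior". That table has separate columns for the mean and the 50% quantile.

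The same list in section 10.6 has "Scenario 4: low-tox followed by high-tox" and "Scenario 5: non-logistic dose-toxicity scenario". Table 10.6:2 names scenario 4 Non-Logistic and scenario 5 Low-High.

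Table 4.1.3:1 gives six potential levels: 40, 120, 360, 720, 1000 (DL5) and 1250 mg. Tables 7.1:2, 10.6:1 and 10.6:2 cover five doses, without 1000 mg, and Table 10.6:3 reports simulations on the five curves of Table 10.6:2.

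**The concern.** Sections 7.1 and 10.6 rest a favourable summary of the design on these tables. A reader takes scenario 1 as the expected case and its row as the performance there: 61.6% on target, 0.2% overdose, 15.5% stopped. If the curve is not the one named, the 61.6% and 15.5% are attributed to the wrong toxicity assumption. If the dose grid is not the one now listed, the 0.2% does not describe the current set of levels. At stake is the accuracy of the stated performance, not the dose given to any patient.

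**Working it through.** **1. Which curve was simulated?** Inputs: Tables 7.1:2 and 10.6:2.

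| Dose (mg) | 40 | 120 | 360 | 720 | 1250 |
|---|---|---|---|---|---|
| Scenario 1 | 0.069 | 0.104 | 0.176 | 0.274 | 0.444 |
| Prior mean | 0.069 | 0.104 | 0.176 | 0.274 | 0.444 |
| Prior median | 0.001 | 0.006 | 0.043 | 0.148 | 0.410 |

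Scenario 1 equals the mean column at all five doses. Drawing from the mixture prior with reference dose 1250 mg gives means 0.068/0.104/0.177/0.276/0.447 and medians 0.001/0.007/0.044/0.150/0.413. So the columns of Table 7.1:2 are labelled correctly and the scenario text is not.

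**2. What follows without simulation.**
- *On target.* On the median curve 720 mg is at 0.148 (below 0.16) and 1250 mg at 0.410 (above 0.33). No tabulated dose is in the target interval, so 61.6% cannot be a result on that curve.
- *Stopping.* Table 10.6:1, scenario 2, shows that 1 DLT in 3 patients at 40 mg leaves no allowed dose (overdose probability 0.278). The chance of at least one DLT in the first n patients is 1 − (1 − p)^n. At p = 0.069 this is 1 − 0.931² = 13.3% and 1 − 0.931³ = 19.3%, which bracket the printed 15.5%. At p = 0.001 it is 0.2% and 0.3%.

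**3. Simulation on five doses.** Section 10.6 does not state the cohort size, so four rules were run, 10,000 trials each: A, two patients and a third after exactly one DLT; B, two and a third after any DLT; C, fixed three; D, two plus one at 40 and 120 mg, then three from 360 mg. Each used overdose probability below 0.25, the increment cap and the section 7.1 MTD rule. B, C and D give the published minimum of 3 patients; A gives 2.
- Mean curve: 55–61% on target, 0.4–0.7% overdose, 14–19% stopped. Rule D gives 61.0% on target and 13.8% stopped against the printed 61.6% and 15.5%. Variants with random cohort sizes gave 51–59% on target.
- Median curve: 0.2–0.3% stopped (0.1–0.4% with random cohort sizes).

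**4. Scenarios 4 and 5.** In Table 10.6:2 their 40 mg rates are 0.040 and 0.001. The first-cohort chance of a DLT is 1 − 0.96² = 7.8% to 1 − 0.96³ = 11.5% for scenario 4, and 0.2–0.3% for scenario 5. The printed stopping rates are 9.6% and 0%. The results follow the table's numbering, so the list is the side that is wrong.

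**5. Reference dose.** Section 7.1 writes 720 mg. Component 1 has means (−0.333, 0.647) and is said to give medians of 0.1% at 40 mg and 20% at 720 mg. The slope is exp(0.647) = 1.910.
- Reference 720 mg: the logit at 720 mg is −0.333, giving 41.8%.
- Reference 1250 mg: −0.333 + 1.910 × ln(720/1250) = −1.387, giving 20.0%; at 40 mg, −0.333 + 1.910 × ln(40/1250) = −6.907, giving 0.1%.

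Only 1250 mg reproduces the stated medians. For the full mixture, 720 mg gives a median of 0.413 at 720 mg, against the printed 0.148.

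**6. Adding 1000 mg.** With the data of scenario 6 in Table 10.6:1 (0 DLTs in 10 patients), the overdose probabilities at 720/1000/1250 mg are 0.024/0.126/0.302 (printed at 720 mg: 0.025). So 1000 mg meets the criterion, and the row no longer shows the highest listed dose the model permits. On the scenario 1 curve the rate at 1000 mg is taken as the model's prior mean, 0.361, which is an assumption because no document prints it.

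| Rule | On target, 5 → 6 doses (%) | Overdose (%) | Patients per trial at true rate ≥ 33% |
|---|---|---|---|
| A | 60.9 → 52.6 | 0.7 → 8.1 | 0.20 → 1.79 |
| B | 60.9 → 53.1 | 0.6 → 8.6 | 0.20 → 1.94 |
| C | 54.8 → 47.3 | 0.4 → 6.0 | 0.13 → 0.99 |
| D | 61.0 → 54.7 | 0.5 → 6.7 | 0.14 → 1.28 |

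A repeat under B, C and D gave 45–55% on target and 7–8% overdose.

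**The case against.** The strongest defence is that little depends on the label. The simulated rates are printed in Table 10.6:2. Section 10.6 itself adds that it expects such stopping to be rare because the starting dose should be safe, and that the DSB could still escalate. The error also makes the design look worse on stopping. All of this stands and limits the harm to a wrong attribution.

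On 1000 mg, Table 7.1:2 claims only selected doses, Table 4.1.3:1 lists potential levels and leaves intermediate ones to the DSB, and this level came in with amendment 2. That also stands: the tables are out of date, not miscalculated. The 6–9% rests on an assumed rate and lies within the overdose range already printed (up to 14.8%, scenario 2). Version 6.0 speaks of two ongoing patients, so dose finding may be over, although the documents do not say so.

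A reader might infer three stronger things that the documents do not support:
- *True on-target performance is zero.* At the prior medians, 720 mg misses the interval by 0.16 − 0.148 = 0.012 and is chosen in 73–78% of simulated trials. At the component 1 medians (20% at 720 mg), on-target selection is 59–67% on five doses and 57–64% on six.
- *The results of scenarios 4 and 5 are misassigned.* Only the names in the list are wrong.
- *Escalation was unsafe.* Section 3.1 bars escalation to any dose that fails the overdose criterion, and the statement that 1250 mg is not allowed after the scenario 6 data still holds (0.302).

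**Conclusion.** The point holds as a reporting error and an incomplete update. Three readings are exact: scenario 1 is the mean curve although the text twice says medians; the names of scenarios 4 and 5 conflict, with the list wrong; and 1000 mg is in none of the model tables. The 61.6% and 15.5% belong to the mean curve. At the medians, no tabulated dose is on target and stopping is below 0.5%. Scenario 3 approximates the medians up to 360 mg and stops in 0% of trials, but it departs at 720 mg (0.180 against 0.148) and at 1250 mg (0.250 against 0.410).

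The 0.2% overdose figure stands for five doses. With 1000 mg included it becomes about 6–9%, and on-target selection about 45–55%. Those two ranges depend on the unstated cohort rule, reference dose 1250 mg and a rate of about 0.36 at 1000 mg. The simulation is approximate: rule D misses the printed on-target figure for scenario 3 by 4.2 points (69.6% against 73.8%).

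**What to change.** 1. In section 10.6, relabel scenario 1 as the prior means, in the list and in the text below Table 10.6:3.
2. Correct the names of scenarios 4 and 5 in the list to agree with Table 10.6:2.
3. Reconcile the reference dose written in section 7.1 (720 mg) with the value that reproduces Tables 7.1:2 and 10.6:1 (1250 mg). SAP section 7.4 takes its model from protocol section 7, so this must be settled before any re-run.
4. Re-run Tables 7.1:2, 10.6:1 and 10.6:3 on the six listed levels, adding the assumed rates at 1000 mg to Table 10.6:2 and stating the cohort rule. Restate the on-target, overdose and stopping figures and the summary sentences in sections 7.1 and 10.6. A prior-median curve would be a useful but optional addition.

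Items 1 and 2 are text only. Item 4 costs a re-run, assuming the sponsor still holds the simulation code. No design change is needed, and simulated mean patient numbers rise by at most about 1.4.
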